 - Arm 1: NTZ 1000 mg (2 x 250 mg tablets BID for day one) and then 1000 mg (2 x 250 mg tablets BID for 4 days) RBV 1200 mg (3 x 200 mg capsules BID day one) and then RBV 800 mg (2 x 200mg capsules BID for 4 days) HCQ 800 mg (2 x 200 mg tablets bid day one) and then HCQ 400 mg (1 x 200 mg tablet BID for 4 days)
 - Arm 2: Placebo for NTZ (2 tablets BID for day one and then 2 tablets BID for 4 days) Placebo for RBV (3 capsules BID day one and then 2 capsules BID for 4 days) Placebo for HCQ (2 tablets bid day one and then 1 tablet BID for 4 days)

Hydroxychloroquine sulfate (HCQ)

One hydroxychloroquine sulfate tablet contains 200 mg of hydroxychloroquine sulfate, which is the equivalent to 155 mg base.

Ribavirin (RBV)

One ribavirin capsule contains 200 mg of ribavirin.

Nitazoxanide (NTZ)

One nitazoxanide tablet contains 500 mg of nitazoxanide.

Take all tablets/capsules with a meal or a glass of milk.

All study drugs should be stored at room temperature 20°-25° (68°-77 °F).

Concomitant Medications & Supportive Guidelines

Study participants can receive full supportive care therapies concomitantly during the study. We will advise rest, fluids, hot/ showers/baths. We will recommend NO antipyretics since they make infections worse by interfering with the generation of fever--which is considered beneficial until it reaches 102 degrees F.

B. Participant Enrollment

We will identify asymptomatic or mildly symptomatic participants who test positive for SARS-CoV-2 from the Rutgers Coronavirus Cohort (RCC) and hospital screening programs, or from the community through advertisements at our medical center, university, and in local publications. The recruiting materials will direct the potential participants to online materials that include information about the trial, consent forms, and a screener questionnaire to assess eligibility. If eligible for the trial, we will answer any questions and provide as much time as needed to review all study materials. The participant may then electronically sign the consent or, as an alternative, wait until the initial visit to re-review and sign the consent. The consenting process will be primarily performed remotely to protect research personnel.

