1.6 Study Variables

A. Primary Outcome:

Viral load at 10 days post randomization

B. Other measures

Age, Gender Race/ethnicity BMI Co-morbidity:

- Diabetes mellitus
- Hypertension
- Chronic bronchitis, emphysema, or chronic obstructive pulmonary disease (COPD)
- Other lung disease
- Coronary artery disease, peripheral artery disease, angina, or heart attack (myocardial infarction)
- Congestive heart failure
- Stroke or transient ischemic attack (TIA)
- Atrial fibrillation
- Cancer other than non-melanoma skin cancer
- Chronic kidney disease (CKD)
- Crohn's disease, ulcerative colitis, or inflammatory bowel disease (IBD)
- Rheumatoid arthritis (RA), psoriasis, systemic lupus, multiple sclerosis, or another autoimmune disorder
- Allergic rhinitis

Medications Symptoms Household infection (confirmed or suspected)

List variables of interest

Treatment Variables:

- Treatment Compliance
- Adverse Events (number/percentage/grade)

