The primary toxicity of ribavirin is hemolytic anemia, which was observed in approximately 13% of all ribavirin/peginterferon alfa-2a- treated participants in clinical trials. Anemia associated with ribavirin occurs within 1 to 2 weeks of initiation of therapy. Because the initial drop in hemoglobin may be significant, it is advised that hemoglobin or hematocrit be obtained pretreatment and at week 2 and week 4 of therapy or more frequently if clinically indicated. Patients should then be followed as clinically appropriate. Caution should be exercised in initiating treatment in any patient with baseline risk of severe anemia (e.g., spherocytosis, history of gastrointestinal bleeding). Fatal and nonfatal myocardial infarctions have been reported in patients with anemia caused by ribavirin. Patients should be assessed for underlying cardiac disease before initiation of ribavirin therapy. Patients with pre-existing cardiac disease should have electrocardiograms administered before treatment and should be appropriately monitored during therapy. If there is any deterioration of cardiovascular status, therapy should be suspended or discontinued. Because cardiac disease may be worsened by drug-induced anemia, patients with a history of significant or unstable cardiac disease should not use ribavirin.

Hepatic Failure

Chronic hepatitis C (CHC) patients with cirrhosis may be at risk of hepatic decompensation and death when treated with alpha interferons, including peginterferon alfa-2a. Cirrhotic CHC patients coinfected with HIV receiving highly active antiretroviral therapy (HAART) and interferon alfa-2a with or without ribavirin appear to be at increased risk for the development of hepatic decompensation compared to patients not receiving HAART.

Hypersensitivity

Severe acute hypersensitivity reactions (e.g., urticaria, angioedema, bronchoconstriction, and

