The participant will then come to the study location at [name] to complete final screening for the trial eligibility. P02 will be measured and 6 lead portable electrocardiogram will be performed; if PO2<92% or QT interval is QTc interval > 450 mSEC the participant will be excluded. Females of childbearing potential will have a urine test to confirm that they are not pregnant.

Inclusion Criteria

- 1. Documented SARS-CoV-2 infection by qPCR assay without symptoms or with mild symptoms consistent with COVID-19 performed within the past 7 days
- 2. Age ≥21

Exclusion Criteria

- 1. COVID-19 symptoms requiring hospitalization
- 2. PO2 < 92%
- 3. Short of breath at time of enrollment
- 4. Retinal eye disease
- 5. Known glucose-6 phosphate dehydrogenase (G-6-PD) deficiency
- 6. Known chronic kidney disease, stage 5 or receiving dialysis
- 7. Current use of:
 - Class 3 AAD (amiodarone, dronaderone, dofetilide, sotalol)
 - Class 1A AAD (procainamide, quinidine, disopyramide)
 - Flecainide
 - SSRI: citalopram (Celexa), Escitalopram (Lexapro)
 - chlorpromazine
 - Cilostazol (Pletal)
 - Donepezil (Aricept)
 - Droperidol
 - Fluoconazole
 - Methadone
 - Ondansetron (Zofran)
 - Thioridazine
 - Macrolides (clarithromycin, erythromycin)
 - Fluroquinolones (ciprofloxacin, levofloxacin, moxifloxacin)
 - Tamoxifen citrate
- 8. Pregnancy or women who are breast feeding
- 9. Inability to tolerate oral medications
- 10. Allergy or prior adverse reaction to either hydroxychloroquine sulfate, ribavirin, or nitazoxanide
- 11. Allergy to adhesives
- 12. QTc interval > 450 mSEC for men and women
- 13. History of Torsade de Pointes VT or prior cardiac arrest or congenital long QT interval
- 14. Non-English-speaking

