The primary toxicity of Ribavirin is hemolytic anemia, which was observed in approximately 13% of all Ribavirin/peginterferon alfa-2a- treated participants in clinical trials. Anemia associated with Ribavirin occurs within 1 to 2 weeks of initiation of therapy. Because the initial drop in hemoglobin may be significant, it is advised that hemoglobin or hematocrit be obtained pretreatment and at week 2 and week 4 of therapy or more frequently if clinically indicated. Patients should then be followed as clinically appropriate. Caution should be exercised in initiating treatment in any patient with baseline risk of severe anemia (e.g., spherocytosis, history of gastrointestinal bleeding)

Fatal and nonfatal myocardial infarctions have been reported in patients with anemia caused by Ribavirin. Patients should be assessed for underlying cardiac disease before initiation of Ribavirin therapy. Patients with pre-existing cardiac disease should have electrocardiograms administered before treatment and should be appropriately monitored during therapy. If there is any deterioration of cardiovascular status, therapy should be suspended or Because cardiac disease may be worsened by drug-induced anemia, patients with a history of significant or unstable cardiac disease should not use Ribavirin.

Hepatic Failure

Chronic hepatitis C (CHC) patients with cirrhosis may be at risk of hepatic decompensation and death when treated with alpha interferons, including peginterferon alfa-2a. Cirrhotic CHC patients coinfected with HIV receiving highly active antiretroviral therapy (HAART) and interferon alfa-2a with or without Ribavirin appear to be at increased risk for the development of hepatic decompensation compared to patients not receiving HAART. In Study NR15961 among 129 CHC/HIV cirrhotic patients receiving HAART, 14 (11%) of these patients across all treatment arms developed hepatic decompensation resulting in 6 deaths. All 14 patients were on NRTIs, including stavudine, didanosine, abacavir, zidovudine, and lamivudine. These small numbers of patients do not permit discrimination between specific NRTIs or the associated risk. During treatment, patients' clinical status and hepatic function should be closely monitored for signs and symptoms of hepatic decompensation. Treatment with peginterferon alfa-2a/Ribavirin should be discontinued immediately in patients with hepatic decompensation.

Hypersensitivity

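### No exclusion criterion covers the cardiac disease for which the protocol's own text says ribavirin should not be used

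*Combined protocol and SAP*

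**What the plan says.** The ribavirin warnings in section 1.7, under Anemia, state that "patients with a history of significant or unstable cardiac disease should not use ribavirin". The adverse-event text in section 4.7 A repeats it: "patients with a history of significant or unstable cardiac disease should not use Ribavirin". The reason given in both places is that anemia caused by the drug can aggravate heart disease. Section 1.7 adds that "Fatal and nonfatal myocardial infarctions have been reported in patients with anemia caused by ribavirin" and instructs that "Patients should be assessed for underlying cardiac disease before initiation of ribavirin therapy".

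The Arm 1 treatment plan in section 1.3 A includes "RBV 1200 mg (3 x 200 mg capsules BID day one) and then RBV 800 mg" daily for the remaining four days. Section 1.5 plans 35 participants per arm, 70 in all.

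Section 4.1 C lists 14 exclusion criteria, numbered without a gap. Item 13 is the only one that names a cardiac history: "History of Torsade de Pointes VT or prior cardiac arrest or congenital long QT interval". Item 12 excludes a QTc above 450 msec, and item 7 excludes current use of listed antiarrhythmic and other drugs.

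**The concern.** The eligibility list is the rule that site staff apply. When the protocol says elsewhere that a group should not receive one of the study drugs, and every active-arm participant is given that drug, the list should screen the group out. Here it does not.

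The existing cardiac items might seem to cover the matter, but they address another mechanism. They guard against QT prolongation and arrhythmia. The ribavirin warning is about anemia in someone whose heart tolerates it poorly, with infarction as the reported consequence. A normal QTc says little about that.

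What is at stake is the safety of a possibly small number of volunteers with mild or no COVID-19 symptoms. The primary analysis is not affected.

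**Working it through.** The check sets texts side by side. The plan states no figure to reproduce, and the only arithmetic is counting and one dose sum.

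**1. Does any of the 14 criteria in section 4.1 C state the warning?**

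| Items | Subject | Covers significant or unstable heart disease? |
|---|---|---|
| 1, 2, 3 | Need for hospital care, low oxygen, breathlessness | Only heart failure that shows as breathlessness or hypoxia |
| 4, 5, 6 | Retinal disease, G-6-PD deficiency, stage 5 kidney disease or dialysis | No |
| 7 | Listed antiarrhythmic and other drugs | Only through drug use |
| 8, 9, 10, 11, 14 | Pregnancy or breast feeding, oral intolerance, drug allergy, adhesive allergy, language | No |
| 12, 13 | QTc limit; torsade, cardiac arrest, congenital long QT | QT and arrhythmia only |

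The rows hold 3 + 3 + 1 + 5 + 2 = 14 items. Items stating the warning: 0 of 14. Items that are cardiac-related: 3 of 14 (7, 12 and 13).

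**2. Is it stated anywhere else?** Sections 1.1 and 1.3 exclude on illness severity, hypoxia, breathlessness and (1.3) drug allergy or intolerance. Section 1.3 B excludes on QT interval, oxygen level and pregnancy test. Section 4.7 B excludes on pregnancy and breast feeding. None adds a heart-disease criterion.

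**3. Test case.** Take a volunteer aged 21 or over with a positive qPCR test within 7 days, mild symptoms, and an infarction a few weeks ago or unstable angina. QTc is 450 msec or less, oxygen is 92% or above, there is no breathlessness, and no item 7 drug is taken. Going through items 1 to 14, none applies. The person is eligible as written and could be allocated to ribavirin.

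**4. Do the pre-treatment assessments close the gap?** Section 1.3 A lists medical history ahead of randomisation, but no cardiac finding in it is named as disqualifying. Section 1.3 B sends the baseline ECG to an electrophysiologist, whose stated task is to work out QT and QTc. Section 1.6 lists 13 comorbidity lines, of which 3 are cardiac: coronary or peripheral artery disease including angina and infarction; heart failure; and atrial fibrillation. All 3 are variables to record, and none is an exclusion. The information needed would be available, but no eligibility rule uses it.

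**5. Exposure.** 35 of 70 planned participants receive ribavirin. The full course is 1200 + 4 × 800 = 4,400 mg per person. This describes what is given and does not measure harm.

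**The case against.** The strongest reply has four parts.

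**It is a warning, not a contraindication.** Section 1.7 has a separate contraindication list for ribavirin, and heart disease is not on it. That is so, and the second statement in section 4.7 A largely repeats the first. But the sentence says outright that these patients should not use the drug. The protocol also turned hydroxychloroquine warnings of no greater force into exclusions: retinal disease, G-6-PD deficiency and tamoxifen use are all on the list.

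**The course is short.** The anemia text draws on ribavirin given with peginterferon. Section 4.7 E points out that participants take only 5 days of drug, and section 1.2 reports no significant hemoglobin fall in short courses for influenza and COVID-19. This lowers the risk and moderates the rating. Nowhere does the protocol say that the cardiac warning is set aside on that ground, and section 1.7 also states that "Anemia associated with ribavirin occurs within 1 to 2 weeks of initiation of therapy".

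**Participants are closely monitored.** The same warning allows for treating people with pre-existing heart disease under ECG and monitoring, and the 10-day telemetry in section 4.7 E is substantial. It stands as mitigation, but the warning treats significant or unstable disease as a separate category that should not get the drug at all.

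**The online screening questionnaire may ask about heart disease.** Its items are not in the documents, so this cannot be settled. An unseen question would not amend the written criteria, but it does limit what can be said about who would in practice be enrolled.

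Three further criticisms might be inferred, and the documents do not support them:

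- That the hemoglobin schedule is inadequate because the first check after baseline is on day 14, after dosing ends. Baseline, day 14 and day 28 match the schedule advised in section 1.7: pretreatment, week 2 and week 4.
- That medical history may be obtained only after dosing, because section 1.3 D allows 24 hours from the start of treatment for baseline forms. That is a data-entry deadline, and section 1.3 A places the history before randomisation.
- That a serious arrhythmia is left without an operational response. Section 4.7 E lists alert triggers with immediate notice to the cardiology team, and section 1.7 B leaves dosing to the treating investigator's instructions.

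**Conclusion.** The point holds as a gap between the protocol's ribavirin warning and its eligibility list: 0 of 14 criteria carry the warning, while all of Arm 1 (planned n = 35) is assigned the drug. Confidence in that reading of the text is high.

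Confidence in its practical impact is moderate. The documents give no prevalence of such disease among the volunteers, so no number of affected participants can be stated. A reader might infer that unstable cardiac patients will be enrolled and harmed. The documents do not show this: the questionnaire is unseen, a clinician reviewing the history may decline to enroll, and the short course and telemetry reduce the hazard.

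The conclusion assumes that the numbered list in section 4.1 C is the complete governing rule and that the warning is meant to apply to a 5-day course, since the protocol does not say otherwise. It has no bearing on sample size, power or the primary analysis. It ranks as a cheap improvement for patient safety.

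**What to change.** Add an exclusion in section 4.1 C that mirrors the ribavirin warning, covering past significant or currently unstable heart disease, with examples such as recent infarction, unstable angina and decompensated heart failure. Put a matching question in the online screening questionnaire. At the baseline visit, confirm the answer from the medical history before randomisation, using the cardiac comorbidity items already listed in section 1.6. Refer doubtful cases to the electrophysiologist who already reads the baseline ECG.

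If the sponsor considers that the warning does not apply to a 5-day course, the alternative is to say so in section 4.7 with the reason, so that the eligibility list and the risk text agree.

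The cost is one criterion, one question and a short check at a visit that already takes place. The downside is slightly fewer eligible volunteers for the 70 planned. No statistical quantity changes.

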4.2 Secondary Participants

N/A

4.3 Number of Participants

A. Total Number of Participants 70

B. Total Number of Participants If Multicenter Study

All participants will be enrolled at Rutgers, Robert Wood Johnson Medical School.

C. Feasibility

Given the current incidence rate of SARS-CoV-2 positivity, we anticipate that enrollment will be completed within 2-6 months.

4.4 Consent Procedures

A. Consent Process

Location of Consent Process

Eligible individuals will complete the consent online following discussion with research coordinators by telephone. Remote consent will be utilized to protect the safety of the research personnel and others. At the baseline visit, the study staff will review the consent document and study procedures, answer any remaining questions, confirm the participant's signature, and also sign the consent.

Ongoing Consent

Participants will undergo intensive follow-up over the 28 day study period, particularly over the first days of active treatment. There will not be ongoing written informed consent obtained, but study staff will make it clear that participants may ask questions about the research or cease their participation at any time.

Individual Roles for Researchers Involved in Consent

All consent will be done online by participants (see 1.3A for details) or by the NJ ACTS and other RBHS clinical research coordinators who conduct the study visits.

Consent Discussion Duration

It is anticipated that consent will take approximately 30 minutes to complete. However, we recognize that in some cases, additional time may be needed to answer questions or address concerns with a study team member. We will answer any questions and provide as much time as needed to review all study materials.

Coercion or Undue Influence

Participants self-initiate interest in study participation by completing the online screening survey. We will make it clear that participation is voluntary and that electing not to participate will not impact clinical care or employment status.

Participant Understanding

At the time the research coordinators obtain the electronic consent, they will query to the participant to be certain they understand they questionnaire completion and specimen collection obligations. Similarly, research coordinators will verify the understanding of these procedures of participants who completed an online eConsent before proceeding with biospecimen collection.

B. Waiver or Alteration of Consent Process N/A

C. Documentation of Consent

Documenting Consent

Prospective participants who are deemed eligible after completing the online screening survey may read through the consent form. Study staff will contact each individual who provides their contact information and express interest in participation. The consent, eligibility and exclusion criteria and study procedures will be reviewed, and questions will be answered. The participant will may then electronically sign the consent or, as an alternative, wait until the initial visit to rereview and sign the consent. The consent will be also be signed by the person obtaining consent. The signed consent will be stored in the REDCap database. The consenting process will be primarily performed remotely to protect research personnel.

Waiver of Documentation of Consent (i.e., will not obtain participant's signature) N/A

4.5 Special Consent/Populations

A. Minors-Participants Who Are Not Yet Adults

N/A

- B. Wards of the State N/A
- **C.** Non-English-Speaking Participants We will only enroll English-speaking participants.
- D. Adults Unable to Consent / Decisionally Impaired Adults N/A

4.6 Economic Burden and/or Compensation for Participants

A. Expenses

The study drugs will be provided at no charge. At the initial visit we will provide each participant with a Zio AT mobile cardiac telemetry device. Participants will return the device at their day 28 visit. Study participants will not be charged for the cost of any research procedures which are conducted as part of this study. Participants and/or their insurance carriers (or Charity Care in the absence of insurance) will be expected to pay for the standard of care costs related to COVID-19 treatment and follow-up and for any other medical treatment (e.g., drug reactions) they require.

B. Compensation/Incentives

Participants will receive a ClinCard at the initial study visit, which will be preloaded with money to pay for that day's parking. On the day 14 and 28 day visits, we will add money to that card to cover the parking costs on those days as well.

We will add additional money to the card at the final (day 28) study visit (maximum amount \$50). The amount of they receive will be based on completion of the study tasks: \$25 for completing all of the self-collected specimens (days 3, 6, & 10) and \$25 for completing both the day 24 and day 28 (final) study visit and returning ZioAT monitoring device.

Participants will also keep the thermometer and the pulse oximeter provided at the initial study visit,

C. Compensation Documentation

None

4.7 Risks of Harm/Potential for Benefits to Participants

A. Description of Risks of Harm to Participants

Reasonably Foreseeable Risks of Harm

Hydroxychloroquine Sulfate Adverse Events:

The package labeling does not provide as clear a percent incidence as modern labels since hydroxychloroquine is an old medication. The following Council for International Organizations of Medical Sciences (CIOMS) frequency rating is used, when applicable: Very common \geq 10 %; Common \geq 1 and <10 %; Uncommon \geq 0.1 and <1 %; Rare \geq 0.01 and <0.1 %; Very rare < 0.01 %; Not known (frequency cannot be estimated from available data).

Blood and lymphatic system disorders

Not known: Bone marrow depression, anemia, aplastic anemia, agranulocytosis, leucopenia, and thrombocytopenia (see Warnings and Precautions, Hematologic).

• Cardiac disorders

Not known: Cardiomyopathy, which may result in cardiac failure and in some cases a fatal outcome. Chronic toxicity should be considered when conduction disorders (bundle branch block/ atrioventricular heart block) as well as biventricular hypertrophy are found. Drug discontinuation may lead to recovery (see Warnings and Precautions, Cardiovascular, Drug Interactions, and Symptoms and Treatment of Over dosage). Hydroxychloroquine prolongs the QT, PR and/or QRS intervals which may lead to an arrhythmia. Ventricular arrhythmias and torsade de pointes have been reported in patients taking hydroxychloroquine (see Warnings and Precautions, Cardiovascular, Drug Interactions, and Symptoms and Treatment of Over dosage).

• Ear and labyrinth disorders

*Uncommon*: \ge 0.1 and < 1 %: Vertigo, tinnitus. *Not known*: Hearing loss, including cases of irreversible hearing loss.

• Eye disorders

Common: \geq 1 and <10 %: Blurring of vision due to a disturbance of accommodation which is dose dependent and reversible (see WARNINGS AND PRECAUTIONS, Ophthalmologic).

Uncommon: ≥ 0.1 and < 1 %: Maculopathies, which may be irreversible. Retinopathy with changes in pigmentation and visual field defects (see Warnings and Precautions, Ophthalmologic). In its early form it appears reversible upon discontinuation of the drug. If allowed to develop however, there may be a risk of progression even after treatment withdrawal. Patients with retinal changes may be asymptomatic initially, or may have scotomatous vision with paracentral, pericentral ring types, temporal scotomas, abnormal color visions, reduction in visual acuity, night blindness, difficulty reading and skipping words. Corneal changes including edema and opacities. They are either symptomless or may cause disturbances such as halos around lights especially at night, blurring of vision, vision disturbances, or photophobia. They may be transient or are reversible upon discontinuation of therapy (see Warnings and Precautions, Ophthalmologic). *Not known*: Macular degeneration, which may be irreversible.

Gastrointestinal disorders

Very common: \geq 10 %: Abdominal pain, nausea. Common: Diarrhea, vomiting. These symptoms usually resolve immediately upon reducing the dose or upon stopping the treatment.

• Hepatobiliary disorders

Uncommon: ≥ 0.1 and < 1 %: Abnormal liver function tests. Not known: Fulminant hepatic failure (see Warnings and Precautions, Hepatic/Biliary/Pancreatic).

Immune system disorders

Not known: Urticaria, angioedema, bronchospasm.

• Metabolism and nutrition disorders

Common: \geq 1 and <10 %: Anorexia (usually resolves immediately upon reducing the dose or upon stopping the treatment). Not known: hypoglycemia (see Warnings and Precautions, Endocrine and Metabolism). Hydroxychloroquine may exacerbate porphyria (see Warnings and Precautions, General).

• Musculoskeletal and connective tissue disorders

Uncommon: ≥ 0.1 and < 1 %: Sensori motor disorders. Not known: Skeletal muscle palsies or skeletal muscle myopathy or neuromyopathy leading to progressive weakness and atrophy of proximal muscle groups. Depression of tendon reflexes, abnormal results of nerve conduction tests. Myopathy may be reversible after drug discontinuation, but recovery may take many months (see Warnings and Precautions, Musculoskeletal).

• Nervous system disorders

Common: ≥ 1 and <10 %: Headache. Uncommon: Dizziness. Not known: Convulsions. Extrapyramidal reactions such as: akathisia, dystonia, dyskinesia, gait disturbance, tremor.

• Psychiatric disorders

Common: \geq 1 and <10 %: Affect lability. Uncommon: \geq 0.1 and < 1 %: Nervousness. Not known: Psychosis, suicidal behavior.

• Skin and subcutaneous tissue disorders

Common: ≥ 1 and <10 %: Skin rash, pruritus. Uncommon: ≥ 0.1 and < 1 %: Pigmentary changes in skin and mucous membranes, bleaching of hair, alopecia. These usually resolve readily upon cessation of therapy. Not known: Bullous eruptions (including urticarial, morbilliform, lichenoid, maculopapular, purpuric, erythema annulare centrifugum), toxic epidermal necrolysis, erythema multiforme, Stevens-Johnson syndrome, Drug Rash with Eosinophilia and Systemic Symptoms (Dress syndrome), photosensitivity, exfoliative dermatitis, acute generalized exanthematous pustulosis (AGEP) (see Warnings and Precautions, Skin).

- Risk of Harm from an Intervention on a Participant with an Existing Condition N/A
- Other Foreseeable Risks of Harm N/A
- Observation and Sensitive Information N/A

RIBAVIRIN Adverse Events

Significant adverse reactions associated with Ribavirin/peginterferon alfa-2a combination therapy include severe depression and suicidal ideation, hemolytic anemia, suppression of bone marrow function, autoimmune and infectious disorders, ophthalmologic disorders, cerebrovascular disorders, pulmonary dysfunction, colitis, pancreatitis, and diabetes.

Pregnancy

Ribavirin may cause birth defects and/or death of the exposed fetus. Ribavirin has demonstrated significant teratogenic and/or embryocidal effects in all animal species in which adequate studies have been conducted. These effects occurred at doses as low as one twentieth of the recommended human dose of Ribavirin.

Ribavirin therapy should not be started unless a report of a negative pregnancy test has been obtained immediately prior to planned initiation of therapy. Extreme care must be taken to avoid pregnancy in female patients and in female partners of male patients. Patients should be instructed to use at least two forms of effective contraception during treatment and for 6 months after treatment has been stopped. Pregnancy testing should occur monthly during Ribavirin therapy and for 6 months after therapy has stopped.

Anemia

The primary toxicity of Ribavirin is hemolytic anemia, which was observed in approximately 13% of all Ribavirin/peginterferon alfa-2a- treated participants in clinical trials. Anemia associated with Ribavirin occurs within 1 to 2 weeks of initiation of therapy. Because the initial drop in hemoglobin may be significant, it is advised that hemoglobin or hematocrit be obtained pretreatment and at week 2 and week 4 of therapy or more frequently if clinically indicated. Patients should then be followed as clinically appropriate. Caution should be exercised in initiating treatment in any patient with baseline risk of severe anemia (e.g., spherocytosis, history of gastrointestinal bleeding)

Fatal and nonfatal myocardial infarctions have been reported in patients with anemia caused by Ribavirin. Patients should be assessed for underlying cardiac disease before initiation of Ribavirin therapy. Patients with pre-existing cardiac disease should have electrocardiograms administered before treatment and should be appropriately monitored during therapy. If there is any deterioration of cardiovascular status, therapy should be suspended or Because cardiac disease may be worsened by drug-induced anemia, patients with a history of significant or unstable cardiac disease should not use Ribavirin.

Hepatic Failure

Chronic hepatitis C (CHC) patients with cirrhosis may be at risk of hepatic decompensation and death when treated with alpha interferons, including peginterferon alfa-2a. Cirrhotic CHC patients coinfected with HIV receiving highly active antiretroviral therapy (HAART) and interferon alfa-2a with or without Ribavirin appear to be at increased risk for the development of hepatic decompensation compared to patients not receiving HAART. In Study NR15961 among 129 CHC/HIV cirrhotic patients receiving HAART, 14 (11%) of these patients across all treatment arms developed hepatic decompensation resulting in 6 deaths. All 14 patients were on NRTIs, including stavudine, didanosine, abacavir, zidovudine, and lamivudine. These small numbers of patients do not permit discrimination between specific NRTIs or the associated risk. During treatment, patients' clinical status and hepatic function should be closely monitored for signs and symptoms of hepatic decompensation. Treatment with peginterferon alfa-2a/Ribavirin should be discontinued immediately in patients with hepatic decompensation.

Hypersensitivity

Severe acute hypersensitivity reactions (e.g., urticaria, angioedema, bronchoconstriction, and anaphylaxis) have been observed during alpha interferon and Ribavirin therapy. If such a reaction occurs, therapy with peginterferon alfa-2a and Ribavirin should be discontinued immediately, and appropriate medical therapy instituted. Serious skin reactions including vesiculobullous eruptions, reactions in the spectrum of Stevens-Johnson Syndrome (erythema multiforme major) with varying degrees of skin and mucosal involvement and exfoliative dermatitis (erythroderma) have been reported in patients receiving peginterferon alfa-2a with and without Ribavirin. Patients developing signs or symptoms of severe skin reactions must discontinue therapy.

Pulmonary Disorders

Dyspnea, pulmonary infiltrates, pneumonitis, pulmonary hypertension, and pneumonia have been reported during therapy with Ribavirin and interferon. Occasional cases of fatal pneumonia have occurred. In addition, sarcoidosis or the exacerbation of sarcoidosis has been reported. If there is evidence of pulmonary infiltrates or pulmonary function impairment, patients should be closely monitored and, if appropriate, combination Ribavirin/peginterferon alfa-2a treatment should be discontinued.

Bone Marrow Suppression

Pancytopenia (marked decreases in RBCs, neutrophils, and platelets) and bone marrow suppression have been reported in the literature to occur within 3 to 7 weeks after the concomitant administration of pegylated interferon/Ribavirin and azathioprine. In this limited number of patients (n=8), myelotoxicity was reversible within 4 to 6 weeks upon withdrawal of both HCV antiviral therapy and concomitant azathioprine and did not recur upon reintroduction of either treatment alone. peginterferon alfa-2a, Ribavirin, and azathioprine should be discontinued for pancytopenia, and pegylated interferon/Ribavirin should not be re-introduced with concomitant azathioprine.

Pancreatitis

Ribavirin and peginterferon alfa-2a therapy should be suspended in patients with signs and symptoms of pancreatitis and discontinued in patients with confirmed pancreatitis.

Impact on Growth in Pediatric Patients

During combination therapy for up to 48 weeks with peginterferon alfa-2a plus Ribavirin, growth inhibition was observed in pediatric participants 5 to 17 years of age. Decreases in weight for age z-score and height for age z-score up to 48 weeks of therapy compared with baseline were observed. At 2 years post-treatment, 16% of pediatric participants were more than 15 percentiles below their baseline weight curve and 11% were more than 15 percentiles below their baseline height curve.

The available longer term data on participants who were followed up to 6 years post-treatment are too limited to determine the risk of reduced adult height in some patients.

NITAZOXANIDE Adverse Events

Gastrointestinal

Gastrointestinal side effects have included abdominal pain (6.6% to 7.8%), diarrhea (2.1% to 4.2%), and nausea (3%). Side effects occurring in less than 1% of patients have included vomiting, anorexia, flatulence, dyspepsia, constipation, dry mouth, and thirst.

The incidence of gastrointestinal side effects may be dose related. Abdominal pain, diarrhea and discolored urine occurred more often in participants receiving higher doses (1 gram twice daily).

Nervous system

Nervous system side effects have included headache (3.1%). Dizziness, somnolence, insomnia, tremor, and hypesthesia have been reported by less than 1% of the patients.

Other

Adverse effects affecting the body as a whole have included asthenia, fever, pain (pelvic/back), flu syndrome, earache, and chills in less than 1% of patients.

Metabolic

Metabolic side effects have included increased creatinine and SGPT in less than 1% of patients.

Dermatologic

Dermatologic side effects have included pruritus, rash, and sweat in less than 1% of patients.

Ocular

Ocular side effects have included pale yellow eye discoloration (<1%).

Respiratory

Respiratory side effects have included epistaxis, rhinitis, lung disease, and pharyngitis.

Genitourinary

Genitourinary side effects have included discolored urine, dysuria, amenorrhea, metrorrhagia, and edema labia.

General

In general, side effects have been mild and transient in nature. The most frequent side effects have included abdominal pain, diarrhea, vomiting, and headache, and the rates of occurrence were not significantly different from placebo.

Musculoskeletal

Musculoskeletal side effects have included myalgia, leg cramps, and spontaneous bone fracture.

Cardiovascular

Cardiovascular side effects have included tachycardia, syncope, and hypertension.

Hematologic

Hematologic side effects have included anemia and leukocytosis.

Renal

Renal side effects have included kidney pain.

B. Procedures which Risk Harm to Embryo, Fetus, and/or Pregnant Participants Women who are pregnant or unwilling to stop breast feeding are excluded from this trial due to the absence of data which demonstrates that this therapy changes morbidity or mortality.

The US FDA labelling for hydroxychloroquine sulcate risk states the following: Teratogenic Effects: Human pregnancies resulting in live births have been reported in the literature and no increase in the rate of birth defects has been demonstrated. Embryonic deaths and malformations of anophthalmia and microphthalmia in the offspring have been reported when pregnant rats received large doses of chloroquine.

Nursing Mothers: Caution should be exercised when administering PLAQUENIL to nursing women. It has been demonstrated that hydroxychloroquine administered to nursing women is excreted in human milk and it is known that infants are extremely sensitive to the toxic effects of 4-aminoquinolines."

The US FDA Labelling for ribavirin states the following: may cause birth defects and/or death of the exposed fetus. Ribavirin has demonstrated significant teratogenic and/or embryocidal effects in all animal species in which adequate studies have been conducted. These effects occurred at doses as low as one twentieth of the recommended human dose of Ribavirin. Ribavirin therapy should not be started unless a report of a negative pregnancy test has been obtained immediately prior to planned initiation of therapy. Extreme care must be taken to avoid pregnancy in female patients and in female partners of male patients.

All patients must be made fully aware of the information relating to the potential for reproductive toxicity as detailed in the Informed Consent Form. Patients of childbearing potential and their

partners, who are sexually active, must agree to the use of two highly effective forms of contraception throughout their participation in the study and for 6 months after last dose of study drug(s).

Women of childbearing potential

